1.3 Schedule of Activities

Table 1 summarizes the SoA at screening for all participants. **Table 2** and **Table 3** summarize the SoA during the main study for neonates (modified sample collection) and non-neonates, respectively.

Table 1 Schedule of Activities: Screening Period (All Participants)

Procedure/study day	Day -7 to Day 1 ^a	For details, see section:
Informed consent/assent	X	5.1
Assignment SID number ^b	X	6.3
Demographics and risk categorization	X	5.1
Medical history	X	NA
Complete physical examination, including height and weight	X	8.2.1
Vital signs (including pulse oximetry)	X	8.2.2
Triple 12-lead ECG	X	8.2.3
Serum chemistry, hematology, urinalysis ^c	X	8.2.4

Table 1 Schedule of Activities: Screening Period (All Participants)

Procedure/study day	Day -7 to Day 1 ^a		For details, see section:
Coagulation	X		8.2.4
Urine pregnancy test (post-pubertal females only) ^d	X		8.2.4.5
Assessment of SAEs	X		8.3
Concomitant medications	X		6.5
Serum sample for SARS-CoV-2 serology (anti-nucleocapsid) testing (all participants other than neonates)	X		8.5.3.2
Verify eligibility criteria	X		5.1, 5.2
Screening criteria specific to each cohort	Cohort 1 Pre-exposure prophylaxis	Cohorts 2 and 3 Treatment of COVID-19	For details, see section:
Documented SARS-CoV-2 RT-PCR test taken \leq 3 days before Day 1 ^c OR Rapid SARS-CoV-2 antigen test (for assignment to study cohorts) per local standard of care authorized for screening or diagnosis	X (negative)	X (positive)	8.6.1
COVID-19 Symptom screen	NA	X (Yes)	5.1

^a Screening activities may be collected over more than one visit during the 7-day screening window if necessary; if screening and dosing occur at the same visit, only one evaluation is required, unless otherwise specified. The sample taken closest to dosing and prior to dosing is considered the baseline sample.

^b Assigned by the IRT system. See Section [6.3](#) for further information.

^c Collection of urine samples for urinalysis from participants who are unable to provide urine samples is not mandatory provided that a reasonable attempt has been made to collect the samples.

^d If urine tests positive or is indeterminate, a quantitative serum β -hCG will be performed for confirmation before the participant is enrolled in the study. Pregnancy testing is for baseline purposes only, and a participant with a positive urine pregnancy test can still participate in the study.

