Procedure	Treatment and follow-up period							Early discontinuation visit	For details, see section:
	Visit 1	Visit 2	Visit 2A	Visit 3	Visit 4	Visit 5	Visit 6		
Day	1	4, 8, 11 or 15^a	8	31	92	183	366		
Window (days)	NA	± 2	± 3	+ 5	± 5	± 10	± 15		
Targeted physical examination		X		X	X	X	X	X	8.2.1
Vital signs (including pulse oximetry)	X ^b (post dose)	X		X	X	X	X	X	8.2.2
TriPLICATE 12-lead ECG							X	X	8.2.3
Serum chemistry, hematology				X		X	X	X	8.2.4
Coagulation tests				X	X		X	X	8.2.4
Urinalysis ^c				X	X	X	X	X	8.2.4
Pregnancy test – urine (females of childbearing potential only) ^d	X (pre-dose)								8.2.4
Concomitant medications	X	X		X	X	X	X	X	6.5
Verify eligibility criteria	X								5.1, 5.2
IMP administration	X								
Sample for SARS-CoV-2 RT-PCR (central laboratory) ^e	X ^{f, g} (pre-dose)		X ^g						8.6.1
Serum sample for SARS-CoV-2 serology (anti-nucleocapsid) (Cohort 1 only)				X	X	X	X	X	8.5.3.2

Table 3 Schedule of Activities: Treatment and Follow-up Period for Participants Other Than Neonates – Main Study

Procedure	Treatment and follow-up period							Early discontinuation visit	For details, see section:
	Visit 1	Visit 2	Visit 2A	Visit 3	Visit 4	Visit 5	Visit 6		
Day	1	4, 8, 11 or 15 ^a	8	31	92	183	366		
Window (days)	NA	± 2	± 3	+ 5	± 5	± 10	± 15		
Pharmacokinetics, pharmacodynamics, and ADA assessments									
Serum sample for AZD7442 PK assessment	Only participants receiving AZD7442 IV (post dose ^b)	X		X	X	X	X	X	8.5.2
Serum sample for AZD7442 ADA assessment	X (pre-dose)			X	X	X	X	X	8.5.3.1
Serum sample for SARS-CoV-2 nAbs assessment	X (pre-dose)			X	X	X	X	X	8.5.4.1
Nasal sample for exploratory PK assessment		X		X	X	X	X	X	8.5.2.2
Safety assessments									
Post dose observation – 1 hour ⁱ	X								8.3.1
AEs ^j	↔							X	8.3
SAEs, MAAEs, and AESIs ^j	↔							X	8.3

^a Participants will be randomly assigned to have a PK sample taken on one of the following days: Day 4, 8, 11, or 15 (ie, one sample per participant). See Section 6.3 for information.

^b Perform 15 minutes (± 5 minutes) after the IMP injection is complete.

^c Collection of urine samples from participants who are unable to provide urine samples is not mandatory provided that a reasonable attempt has been made to collect the samples.

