Measures will be undertaken to ensure minimal SARS-CoV-2 exposure for site staff as well as study participants according to local requirements. Exclusion and withdrawal criteria are in place to ensure site staff and study participant safety. In Cohort 1 (prophylaxis), a post-baseline SARS-CoV-2 positive result in participants who were SARS-CoV-2 negative at baseline and developed COVID-19 symptoms during the study will be reported as an AE. Measures will be applied at the discretion of the Investigator to minimize further SARS-CoV-2 exposure as much as possible. Guidance for management of participants who wish to receive or parents who wish for their child to receive an authorized vaccine for protection against SARS-CoV-2 during the study is provided.

The study flow chart is presented in [Figure 1](#) and a graphical representation of the recruitment and safety reviews is presented in [Figure 2](#). The SoA displaying assessments/tasks and time points is presented in Section [1.3](#). Following a screening evaluation, which can be conducted over one or more visits between Day -7 to Day 1, participants will receive a single dose of IMP. After administration of the dose of IMP on Day 1, participants will be monitored on site for at least one hour for general safety, including injection/infusion site reactions and hypersensitivity reactions (including anaphylaxis). Participants will undergo a follow-up until Study Day 366 for safety, including recording of AEs and SAEs, and collection of blood samples for PK, PD, and ADAs, and exploratory efficacy endpoints. The maximum duration

of the study for each participant, including screening, will be 388 days.

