11 Participants who are symptomatic must be dosed with IMP no more than 7 days from self-reported or observed onset of COVID-19-related symptoms or measured fever, defined as the self-reported date of first reported sign/symptom from the list in [Table 13](#). One or more COVID-19 signs/symptoms must also be present within 24 hours prior to Day 1 to be eligible for inclusion.

12 Oxygenation saturation of \geq 92% obtained at rest by study staff within 24 hours prior to Day 1, unless the potential participant regularly receives chronic supplementary oxygen for an underlying lung condition.

Note that Cohort 2 will only be included if the indication is progressed in adults.

COHORT 3: Participants with severe COVID-19 (treatment):

13 Patients hospitalized with COVID-19 with a time between onset of symptoms and dosing AZD7442 of \leq 7 days

14 Documented positive SARS-CoV-2 RT-PCR test collected \leq 3 days prior to Day 1 or a positive rapid SARS-CoV-2 antigen test at screening.

15 Spontaneous blood ALT/AST levels \leq 5 times the ULN

16 Glomerular filtration rate \geq 30 mL/min/1.73 m²

Note that Cohort 3 will only be included if the indication is progressed in adults.

Route of Administration:

Participants will receive IM AZD7442 unless they meet any of the following criteria for IV administration:

- 17 The participant has severe COVID-19
- 18 IM dosing is contraindicated due to:
 - (a) Thrombocytopenia (< 120000 cells/mm³)
 - (b) Coagulation defects
 - (c) Any other condition that would compromise the absorption of AZD7442 or safety of the participant (eg, hypovolemic shock, myopathy, muscular atrophy, active infection other than SARS-CoV-2, cellulitis, and dermatitis at the injection site).
- 19 Any other participant for whom the enrolling physician considers an IV infusion the most appropriate route of administration.

Informed Consent

- 20 Provision of a signed and dated written informed consent form prior to any mandatory study specific procedures, sampling, and analyses. Informed assent is to be provided by participants who are capable of forming an opinion and assessing the information given to him or her; informed consent must be provided by the participant's legal guardian.

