5.2 Exclusion Criteria

Participants are excluded from the study if any of the following criteria apply:

Medical Conditions

- 1 Cohort 1: Significant infection or other acute illness, including fever > 100 °F (> 37.8 °C) on the day prior to or day of receiving AZD7442.
- 2 History of infection with SARS-CoV-1 or MERS-CoV.
- 3 Cohorts 1 and 2: Current need for immediate medical attention in an emergency room service in the clinical opinion of the site Investigator or current need for hospitalization ([Appendix E](#)) in the following circumstances:
 - (a) Due to progressive COVID-19 as this implies severe disease (an exception is participants hospitalized with mild-moderate COVID-19 as a precautionary measure for isolation/infection prevention or for the purpose of conducting study procedures).
 - (b) For any underlying medical condition that requires hospitalization (suggestive of an unstable medical condition) with the following exceptions:
 - Neonates aged \geq 29 weeks GA to < 1 month in their birth hospitalization when discharge is expected within 7 days after receiving AZD7442.

- Children hospitalized for maintenance chemotherapy administration (induction, reinduction, relapse chemotherapy excluded). AZD7442 administration is to occur a minimum of 2 hours post chemotherapy administration (including any hydration or blood products) or post the institutional standards for observation after chemotherapy administration, whichever is longer. Only children who, in the opinion of the investigator, are at low risk for a hypersensitivity reaction to administration of chemotherapy or blood products should be considered for same day administration of AZD7442 during hospitalization for maintenance chemotherapy.

- 4 Requirement for mechanical ventilation or extracorporeal membrane oxygenation or anticipated impending need for mechanical ventilation at baseline for treatment of COVID-19 (CPAP and high flow O₂ is permitted).
- 5 Known history of allergy or reaction to any component of the study drug formulation.
- 6 Previous hypersensitivity, injection/infusion-related reaction, or severe adverse reaction following administration of a mAb for any indication.
- 7 Any co-morbidity requiring surgery within 7 days prior to study entry, or that is considered life-threatening in the opinion of the site Investigator within 30 days prior to study entry.

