
Mild local reactions (During and post injection/infusion and hypersensitivity)
 
Mild injection/infusion site reactions such as redness, mild swelling, pain at the injection site or headache, nausea, non-pruritic rash, or mild hypersensitivity reactions including localized at the injection site or generalized cutaneous reactions such as mild pruritus, flushing, rash, dizziness, headache, ≤ 20 mmHg change in systolic BP from pre-administration measurement.
	
Evaluate participant, including close monitoring of vital signs.
 
At the discretion of the Investigator, treat participant, for example, with:
 
Localized cold pack or heat to the injection site. If more generalized reaction:
 
 • Diphenhydramine or equivalent and/or • Acetaminophen or equivalent dose of paracetamol and/or • Topical antihistamines and/or low-potency topical corticosteroid preparations and/or • Anti-nausea medication, as needed. 
Doses and route of administration as per local standard of care.
	
Pause or hold additional IMP injection immediately.
 
At the discretion of the Investigator, resume current IMP administration under observation.

Moderate reactions (during or immediately post injection)
 
Injection/infusion site reaction such as those listed above under mild reactions but excluding moderate hypersensitivity reactions (see below).
	
Evaluate participant, including close monitoring of vital signs.
 
Treat participant, for example, with:
 
 • Normal saline IV and/or • Diphenhydramine 50 mg IV or equivalent and/or • Acetaminophen 500 to 650 mg or equivalent dose of paracetamol and/or • Anti-nausea and/or antiemetic intramuscular, as needed. 
Doses and route of administration as per local standard of care.
	
Stop or hold additional IMP administration immediately.
 
At the discretion of the Investigator, resume current IMP administration under observation.

Moderate hypersensitivity reactions
 
Reactions which may include generalized rash or urticaria, palpitations, chest discomfort, shortness of breath, hypo- or hypertension with
	
Evaluate participant, including close monitoring of vital signs.
 
Treat participant, for example, with:
 
 • Normal saline IV and/or 	
Stop IMP administration immediately.

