Table 19 An Approach to Management of Anaphylactic, Hypersensitivity, and Post Injection/Infusion Reactions

Severity of symptoms	Treatment	Investigational product
> 20 mmHg change in systolic BP from pre-infusion measurement.	
 Diphenhydramine or equivalent and/or Acetaminophen or equivalent dose of paracetamol and/or IV corticosteroids, such as hydrocortisone or methylprednisolone. 
Doses and route of administration as per local standard of care.
	

Severe Above plus fever with rigors, hypo- or hypertension with ≥ 40 mmHg change in systolic BP, signs of end-organ dysfunction (eg, symptomatic hypotension such as hypotonia, syncope, incontinence, seizure) from pre-infusion measurement, or wheezing, angioedema, or stridor
 
OR
 
Life-threatening Defined as a reaction that is life-threatening and requires pressor and/or ventilator support or shock associated with acidemia and impairing vital organ function due to tissue hypoperfusion
	
Evaluate participant, including close monitoring of vital signs. Maintain airway, oxygen if available. Treat participant immediately, for example with:
 
 Normal saline IV Epinephrine for bronchospasm, hypotension unresponsive to IV fluids, or angioedema IV corticosteroids, such as hydrocortisone or methylprednisolone Diphenhydramine or equivalent Acetaminophen or equivalent dose of paracetamol 
Doses and route of administration as per local standard of care. Call emergency medical transport for transport to emergency hospital based on judgment of the Investigator. Grade 3 wheezing, hypotension or angioedema is unresponsive to single dose of epinephrine Grade 4 event At the discretion of the Investigator
	
Stop IMP administration immediately. Do not resume current dosing. Permanently discontinue IMP administration. Consider need for additional oral antihistamine administration or oral corticosteroid administration to prevent reoccurrence of symptoms over subsequent 2 to 3 days.

BP, blood pressure; IMP, investigational medicinal product; IV, intravenous;

RCH 2021

The Royal Children's Hospital (RCH) Melbourne. Clinical Practice Guidelines. Anaphylaxis.
Available from: https://www.rch.org.au/clinicalguide/guideline_index/Anaphylaxis/ Accessed
22 September 2021.

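### Visit 1 vital signs are scheduled only after dosing, so the baseline for the Day 1 change, a primary safety measure, can be a screening reading up to 7 days old

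*Protocol*

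**What the plan says.** **Schedule.** In Protocol 1.3, Tables 2 (neonates) and 3 (all others), the Visit 1 vital-signs cell is marked post dose only. The footnote reads "Perform 15 minutes (± 5 minutes) after the IMP injection is complete". Table 1 has vital signs once in the screening period. Protocol 4.1 describes screening as an evaluation "which can be conducted over one or more visits between Day -7 to Day 1". A footnote to Table 1 allows a single evaluation when screening and dosing fall at the same visit. Protocol 8.2.2 leaves the timing of vital signs to the schedule.

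**Analysis.** SAP Table 2 lists vital signs among the primary safety endpoints. SAP 4.2.2.3 summarizes observed values and changes from baseline by time point. SAP 3.3.2 defines baseline as the last non-missing value before dosing. It names screening readings as eligible and sets no maximum age.

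**Other passages that use a pre-dose reading.**
- Protocol Appendix F, Table 19: the mild row uses "change in systolic BP from pre-administration measurement" and the moderate hypersensitivity row uses "> 20 mmHg change in systolic BP from pre-infusion measurement".
- Protocol 5.2, exclusion 1 (Cohort 1): significant infection or acute illness, including fever, "on the day prior to or day of receiving AZD7442".
- Protocol 5.1, inclusion 12 (Cohort 2): oxygen saturation "obtained at rest by study staff within 24 hours prior to Day 1".
- Protocol 5.1, inclusion 11 (Cohort 2) requires a symptom in the 24 hours before Day 1. Inclusion 6 (Cohort 1) requires no symptoms within 10 days of dosing. The "COVID-19 Symptom screen" row appears only in Table 1, and there it is not applicable to Cohort 1.

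**The concern.** A change from baseline at 15 minutes is meant to show what happened around dosing. If the baseline was taken days earlier, the change also contains ordinary day-to-day variation. It may also contain the course of the illness in Cohort 2, where symptomatic children are dosed within 7 days of onset, and growth and maturation in newborns. The first component widens the spread of the Day 1 change. The other two could shift its mean. With no control group, neither can be separated from an effect of dosing.

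Table 19 raises a second question. It uses the change in systolic pressure from a pre-dose reading as one feature that separates its rows. The schedule does not say where that reading comes from or how old it may be.

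**Working it through.** **1. Reproduce the plan's day count.** Protocol 4.1 gives a maximum of 388 days including screening. Screening 7 + last visit Day 366 + upper visit window 15 = 388. The plan's figure thus allows the full 7 days of screening.

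**2. Age of the last scheduled pre-dose reading.** SAP 3.3.4 defines study day before dosing as the date of the visit minus the date of dosing, and has no Day 0. Day -7 is therefore 7 days before dosing. If the screening vital signs are taken on Day 1, the age is 0 days. The range is 0 to 7 days.

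**3. Timing of the post-dose reading.** 15 - 5 = 10 minutes to 15 + 5 = 20 minutes after dosing. The footnote names only the injection; I read it as covering the infusion too.

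**4. Is the missing pre-dose entry an artefact of the table?** No. In the same Visit 1 column of Table 3, the pregnancy test, the RT-PCR sample, the anti-drug antibody sample and the neutralizing antibody sample are all marked pre-dose. Since 8.2.2 defers to the schedule, following the protocol exactly gives no separate Visit 1 pre-dose reading.

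**5. Set the uses side by side.**

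| Use | Time limit in the text | Can a reading 7 days old serve? | What is missing |
|---|---|---|---|
| Baseline for the Day 1 change (SAP 3.3.2, 4.2.2.3) | None | Yes | A reading near dosing |
| Systolic pressure comparator (Table 19) | None | Not ruled out | A Day 1 slot |
| Fever (exclusion 1) | Day before or day of dosing | No | A row in the schedule |
| Oxygen saturation (inclusion 12) | 24 hours before Day 1 | No | A row in the schedule |
| Symptom present (inclusion 11) | 24 hours before Day 1 | No | A row in the schedule |
| No symptoms (inclusion 6) | 10 days before dosing | No; later days are not covered | A row for Cohort 1 |

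The last four criteria also fall under the eligibility check that Tables 2 and 3 schedule on Day 1.

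**6. How much noise could this add?** The documents give no variability for vital signs, so this is an illustration only. Assume a within-child, between-day standard deviation of systolic pressure of 6 to 10 mmHg, independent readings and no drug effect. The change then has standard deviation √2 × 6 = 8.5 to √2 × 10 = 14.1 mmHg. I have no figure for two readings taken minutes apart, so the excess due to the older baseline is not estimated.

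**7. How many children?** SAP section 2 gives 46 participants in the full analysis set. The documents do not say how many lack a same-day pre-dose reading, so the number is somewhere from 0 to 46.

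**The case against.** The plan allows screening and dosing at one visit, and Protocol 8.6.1 provides the rapid antigen test for same-day cohort assignment. Screening may be split over visits, and SAP 3.3.2 accepts unscheduled pre-dose readings. Many children may therefore have a same-day baseline. The analysis is descriptive, with no hypotheses. Enrolment has ended, so a new schedule entry cannot supply readings for children already dosed. All of this is fair. It limits the size of the problem and shifts the remedy partly to the analysis, but it does not put a pre-dose reading into the schedule.

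A reader might infer more than the documents support:

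- **That a week-old reading can satisfy the fever, oxygen-saturation or symptom criteria.** It cannot. Each has its own window, eligibility is verified again on Day 1, and Protocol sections 5 and 8 bar waivers.
- **That reactions would be misgraded in 2% to 16% of children.** Under the assumption in step 6, the chance of a difference above 20 mmHg is 2 × (1 - Φ(20/8.5)) ≈ 2% to 2 × (1 - Φ(20/14.1)) ≈ 16%. That is chance variation in any child, with or without a reaction. Table 19 concerns children who are having a reaction, and pressure is one feature among several.
- **That the results on adverse events of special interest are distorted.** Table 19 is management guidance and leaves final treatment to the investigator. Adverse event intensity is graded under Protocol 8.3.2 and Appendix B 2, and these events are categorized in the eCRF (SAP 4.2.2.1). No planned analysis uses a Table 19 row.
- **That symptoms starting between screening and dosing will be counted as progression in Cohort 2.** SAP 4.2.5.2 does not name the reference for a new symptom. But adverse events carry start dates, and inclusion 11 requires symptoms to be assessed close to Day 1. The documents do not show that such a miscount would occur.

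**Conclusion.** The point holds for two uses. The baseline for the Day 1 change in vital signs may be 0 to 7 days old when the schedule is followed exactly, and Table 19's pre-dose pressure has no Day 1 slot. The consequence is a noisier, and possibly shifted, Day 1 change in one descriptive component of the primary safety endpoint. Seven days is the worst case. The number of children affected and the added variance cannot be found from the documents.

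For the fever, oxygen-saturation and symptom criteria the finding is narrower: the schedule has no row showing where the required reading is recorded if screening took place earlier. This rests on reading the Visit 1 cell as it stands, which the pre-dose labels elsewhere in that column support.

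**What to change.** **For any further dosing under this protocol.** Change the Visit 1 vital-signs cell in Tables 2 and 3 to pre-dose and post-dose, and name the pre-dose reading as the vital-sign baseline in SAP 3.3.2. The cost is a few minutes on Day 1 with the child already on site, one eCRF time point and a schedule edit.

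**For participants already dosed.** Report the time from each vital-sign baseline to dosing, and present the Day 1 post-dose change separately for those with a same-day pre-dose value. SAP 4.2.2.3 already lists assessment dates and times, and SAP 4.2.8.1 lists administration dates and times, so no new data are needed. The cost is one derived variable and one extra summary. Groups will be small, and SAP 3.3.1 presents full descriptive statistics only if n exceeds 3, so a listing may have to serve for some. This shows how far the problem extends but does not recover readings that were never taken.

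**Reconcile** Protocol Tables 1 to 3, Appendix F Table 19, exclusion 1, inclusions 6, 11 and 12, and SAP 3.3.2, so that each reading a passage relies on has a place in the schedule. No clinical threshold or management rule is proposed.
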